site, the participant will be asked to rate the pain intensity by using an NRS. Static mechanical allodynia will be assessed using Semmes-Weinstein monofilaments. Evoked pain intensity will be rated on an NRS.

- Pain assessments:

Numerical Rating Scale (NRS): Numerical rating scales are widely accepted and used for the measurement of pain intensity. In this study, we will use this scale to assess the subjects' ratings of pain sensation on a scale of 0 (no pain) to 10 (most intense pain imaginable). For pain history, the International SCI Pain Basic Data Set (ISCIIPBDS, version 2.0) will be used.

Session 2-11) BI-tDCS

Participants will undergo 10 study sessions of BI and tDCS, 30 min, during a period of 2-4 weeks (from Monday to Friday) (Sessions 2-11). We will allow for up to 3 missed sessions.

BI procedure: Two types of illusions will be used 15 min each, the rubber hand illusion (RHI) and the walking illusion (WI) to target upper and lower limbs. In the RHI a prosthetic hand will rest inside a box in front of the subject's midline at the same distance in front of the subject's chest as the subject's hand is. The entire box will be covered by a mirror, which prevents the subject from seeing their hand. The procedure requires that participants will only see the rubber hand while stimulated (tactile stimulation by using a paintbrush) and at the same time their hand will be also stimulated but hidden from their view. This will create a visual illusion as the fake hand will be perceived as one's own hand. For the WI participants will sit in their wheelchair and a screen will be placed in front of them, composed by a half mirror (top part) and half projector-screen (bottom part). Participants will be instructed to move their upper body and observe themselves in the mirror, while online a video of a walking person will be projected on the half bottom part of the screen. This will give the illusion of walking. After each illusion we will ask participants questions about the strength of the illusion. We will use the body ownership subscale (5 items) of the 27 items that compose the psychometric perspective of the embodiment after bodily illusion by Longo et al. in 2008 (*Longo et al., 2008*). The 5 items of the questionnaire include questions about the feeling of body ownership of the rubber hand and virtual legs, the response options range from -3 (completely disagree) to +3 (completely agree).

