Risks/discomforts associated with tDCS: the current applied is very weak (2mA) and there are not observed serious adverse effects associated with tDCS. Minor side effects have included (restricted to the electrode location) mild temporary burning or tingling at the site of stimulation, headaches and tiredness (Bikson *et al.*, 2016), it is a safe procedure widely used (see (Nitsche *et al.*, 2003; Poreisz *et al.*, 2007) for more information and safety aspects of tDCS use). It should be noted that other side-effects like nausea and dizziness can happen and also that they have been illustrated to occur at nearly the same rate as sham stimulation (fake stimulation) (Brunoni *et al.*, 2011). These sensations are not painful and go away when stimulation stops. When electrodes are placed too close to the eye, participants may experience phosphenes that go away adjusting the position of electrodes. tDCS it is not a medical device and it is considered a non-significant-risk device, meaning that it is a technique without expectation of any Serious Adverse Effect (Bikson *et al.*, 2016; Fregni *et al.*, 2015). We use standard procedures, which means: no more than 2mA of intensity, not more than 40 min per session, with standard electrodes (pads) that are typically square 5 × 5 cm or 5 × 7 cm (Bikson *et al.*, 2016). It has been extensively used in human research and chronic pain (Pinto *et al.*, 2018).

Please note that there is no scientific evidence that suggests lasting injury or irreversible side-effects from tDCS, all the minor sides effects are temporary.

We will explain participants the device and the possible minor side effects and we will let them familiarizing for short time by applying a very small amount of current before to reach 2mA.

Adverse Events and Serious Adverse Events associated with electrical stimulation:

temporary skin redness, itching, and tingling. Other suggested but rare side-effects of tDCS include headache, nausea, and dizziness. These sensations go away when stimulation stops.

tDCS it is not a medical device and it is considered a non-significant-risk device, meaning

that it is a technique without expectation of any Serious Adverse Effect.

Participants will report to study team if any of these side effects will be experienced, we will keep record of any reported side effect.

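### tDCS side effects are collected only by unsolicited, ungraded report, so harms are likely to be under-counted by an unknown amount

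*Combined protocol and SAP*

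**What the plan says.** The method is in section 7, under the heading on adverse events associated with electrical stimulation. Two groups of effects are listed there: "temporary skin redness, itching, and tingling", and then "Other suggested but rare side-effects of tDCS include headache, nausea, and dizziness". The collection rule follows: "Participants will report to study team if any of these side effects will be experienced", and "we will keep record of any reported side effect".

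The preceding text on tDCS risks, also in section 7, names further effects: "mild temporary burning or tingling at the site of stimulation, headaches and tiredness", and, when an electrode sits too close to the eye, "participants may experience phosphenes that go away adjusting the position of electrodes". It adds a briefing: "We will explain participants the device and the possible minor side effects".

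Straight after the collection rule, section 7 states that if discomfort means stimulation has to stop, nothing collected from that participant will be considered.

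In section 4 the session table has no row for adverse events. Pain assessments appear at Session 1 and Session 12 only. Structured questioning does take place at the treatment sessions, but on another subject: "After each illusion we will ask participants questions about the strength of the illusion". The single sentence on data analysis in section 7 leaves the choice between parametric and non-parametric methods to the data and does not mention safety.

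**The concern.** Under this rule an effect enters the record only if the participant decides to mention it. Mild, brief or unexpected effects are the ones most easily left unsaid, and the prompt points to a list shorter than the protocol's own account of what tDCS can cause. Increased pain is not on the list either, in a trial whose participants all have neuropathic pain.

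Without a fixed time of asking and a severity grade, counts from different participants and sessions do not mean the same thing. The tolerability information that this pilot passes on to a later trial would consist of these counts. A low count could reflect good tolerability or silence, and the data could not separate the two. If participants in one arm were readier to report than in the other, the comparison between arms would also be distorted.

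**Working it through.** The documents give no expected event rate, reporting rate or safety sample size, so there is no planned figure to reproduce. The check compares the relevant texts and then shows how the consequences depend on an assumed reporting share.

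**1. Lists compared.** Effects to which the reporting instruction most naturally refers: redness, itching, tingling, headache, nausea, dizziness. Effects named earlier in section 7 but absent from that list: burning, tiredness, phosphenes. In neither: increased pain.

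**2. Pain.** NPSI, the Pain Basic Data Set, QST and PGIC are placed at Sessions 1 and 12. The Pain Basic Data Set covers the last week, so a rise shortly before Session 12 may show. With treatment spread over 2-4 weeks, an earlier rise that had settled would be known only if volunteered.

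**3. Chance of seeing an effect at all.** Inputs: n = 8 per arm (section 4 table); true per-participant rate p and share of affected participants who report s, both assumed. P(at least one recorded) = 1 - (1 - p*s)^n. For p = 0.20 and s = 1, this is 1 - 0.8^8 = 0.83.

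| Share reporting s | p = 20%, n = 8 | p = 10%, n = 8 | p = 20%, n = 10 | p = 10%, n = 10 |
|---|---|---|---|---|
| 100% | 0.83 | 0.57 | 0.89 | 0.65 |
| 75% | 0.73 | 0.46 | 0.80 | 0.54 |
| 50% | 0.57 | 0.34 | 0.65 | 0.40 |
| 25% | 0.34 | 0.18 | 0.40 | 0.22 |

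The n = 10 columns are shown because section 14 gives a total of 20, not 16; an equal split is assumed.

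**4. Comparison between arms.** Observed rate = true rate x share reporting. Assume true rates of 50% active and 30% sham (difference 20 points, ratio 50/30 = 1.67).

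| Share reporting, active / sham | Observed rates | Difference (points) | Ratio |
|---|---|---|---|
| 100% / 100% | 50% v 30% | 20 | 1.67 |
| 75% / 75% | 37.5% v 22.5% | 15 | 1.67 |
| 50% / 50% | 25% v 15% | 10 | 1.67 |
| 25% / 25% | 12.5% v 7.5% | 5 | 1.67 |
| 50% / 75% | 25% v 22.5% | 2.5 | 1.11 |
| 75% / 50% | 37.5% v 15% | 22.5 | 2.50 |

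Equal under-reporting shrinks the difference and leaves the ratio unchanged. Unequal under-reporting moves the ratio in either direction.

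**5. Sample size as a separate limit.** Two-sided Fisher test, 8 per arm: for 5 v 0 events, p = 2 x C(8,5)/C(16,5) = 112/4368 = 0.026; for 4 v 0, p = 2 x C(8,4)/C(16,4) = 140/1820 = 0.077. At least 5 v 0 is needed for p <= 0.05, so formal comparison is weak even with perfect recording.

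**6. The discomfort rule.** Suppose 2 of 8 participants in an arm have an effect (25%) and one of them is stopped for discomfort. If that person's data are set aside, the table shows 1 of 7 (14%). The participant removed is the one who tolerated stimulation least.

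**The case against.** Safety is not among the objectives or endpoints, the trial is a pilot, and the sample is too small to test a difference in harms. All of that is true. It limits what may be concluded from the counts, but it does not make incomplete counts acceptable when complete ones are cheap.

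Participants are told beforehand about possible side effects, and that briefing may cover more than the short list. Reporting is therefore primed, though not solicited.

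Repeated sessions give repeated chances to report. If an effect recurs at three sessions and each is reported independently, the share of affected participants counted is 1 - (1 - r)^3, where r is the share reported per session: 58%, 88% and 98% for r = 25%, 50% and 75%. This softens the under-count of participants for recurrent effects. It does not help with one-off effects or with people who never volunteer, and it does not restore counts by session or severity.

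The discomfort rule may be meant for outcome data only, with the side-effect record kept. The text does not say so.

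Some stronger inferences are not supported:

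- That only listed effects are recorded. The same sentence says any reported effect is kept; the restriction lies in what participants are asked to report.
- That any rise in pain goes unseen. A rise still present at Session 12 is measured, and PGIC has levels for worsening.
- That the arms cannot be compared. One reporting method is described for both arms, and sham follows the active procedure apart from the early switch-off. Unequal reporting is possible but not shown.
- That a confidence limit for zero events in 8 measures the problem. It reflects sample size and would be the same under the fix.

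**Conclusion.** The point holds as a weakness of method: side effects are gathered by unsolicited, untimed and ungraded report, prompted by an incomplete list. Under-counting is likely, and transient pain increases between the assessment visits are the clearest gap. Its amount cannot be derived from the documents, and the tables above rest on assumed rates and reporting shares. Over the range shown, a true 20% effect would be recorded at least once in an arm of 8 with probability 0.34 to 0.83, and a true 20-point difference would appear as 5 to 20 points under equal reporting. Bias in the ratio requires reporting that differs by arm. Read literally, the rule for participants stopped for discomfort adds to the under-count. A descriptive comparison between arms remains possible, though weak. This should be changed, but it does not invalidate the trial.

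**What to change.** After every stimulation session, ask all participants in both arms the same short checklist: every effect named in section 7 (redness, itching, tingling, burning, headache, tiredness, nausea, dizziness, phosphenes), increased pain, and one open item, each with a severity grade. It can be asked alongside the illusion questions. Add a row for it to the session table in section 4.

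Tabulate the results by arm for everyone who received any session, including those who stop. Reconcile the data-exclusion rule for participants stopped for discomfort with the safety record, so that it does not apply to side-effect data.

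The cost is about one to two minutes per session on a form, with no extra visit or staff. More mild events will be recorded, which is why the severity grade is needed. A checklist does not remove the influence of what participants believe they received, but it puts the same question to everyone at the same time.

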General: Candidates will be excluded if they have: (1) major psychiatric disease/disorder (self-reported); (2) a significant neurological trauma besides SCI (3) a recent (one-year) history of alcohol or drug abuse (self-reported); (4) any other medical conditions in which transcranial DCS is relatively contraindicated, such as pregnancy, epilepsy and/or seizures.

Arms and Interventions

| Groups | Arms and Interventions | Intervention |
|---------------------------|------------------------|---------------------------------|
| Group 1 (8 SCI with Pain) | Experimental arm | BI-tDCS over 2-4 weeks |
| Group 2 (8 SCI with Pain) | Sham comparator arm | BI-inactive tDCS over 2-4 weeks |

Procedures Involved

Participants will complete Pain/Sensory examination, EEG recording at rest and BR measures before BI and tDCS exposure (or BI and inactive tDCS: sham) (PRE-Session 1), then they will undergo 10 study sessions of BI and tDCS (or sham), 30 min, during a period of 2-4 weeks (from Monday to Friday) (Sessions 2-11). Finally, they will complete Pain/Sensory examination, EEG recording at rest and BR measures after BI and tDCS exposure (or sham) (POST- Session 12). See details below.

| Session 1 - Baseline | Sessions 2-11 | Session 12 |
|--|---------------|--------------------------------|
| Screening: Information on Injury; Age; Sex; BMI, Inclusion/Exclusion criteria listed above | BI-tDCS | - |
| BR measures: Computer task: mental rotation of body parts | | BR measures |
| EEG recording at rest | | EEG recording at rest |
| Sensory and Pain Assessment: QST; NPSI; ISCPBDS; PGIC | | Sensory and Pain Assessment |
| Other Questionnaires: PGWBI; BDI; CDS, Illusion measure | | Other Questionnaires |

PRE-Session (1). This session is done in a single visit of a duration of three hours, however, if necessary, we will divide the tests in 2 visits over 1 week, to meet participants' need.

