tDCS: Direct current will be delivered from a battery-driven, constant current stimulator (TCT Research Version, Hong Kong) using saline-soaked surface sponge electrodes (35 cm²). The anode will be placed over P4 (EEG 10/20 system) to target the right Posterior Parietal Cortex (rPPC), and the cathode over the contralateral supraorbital area. This electrode position is chosen because rPPC has been shown to be involved in

multisensory integration, BR and localization of somatic stimuli (*Azañón et al., 2010; De Vignemont, 2007; Makin et al., 2008; Wertheim et al., 2020*). However, consistent with other tDCS studies on pain (*Soler et al., 2010*), where the site of stimulation is contralateral to the painful body-part, if participants have not bilateral pain and the painful site involves only the right side of the body, the anodal electrode will be placed on P3, the left Posterior Parietal cortex (lPPC), and be therefore contralateral to the painful body-part. A constant current of 2mA intensity will be applied for 30 min during the BI (15 min RHI plus 15 min WI). The duration of the stimulation has been chosen as used in previous works (*Mameli et al., 2014; Ouellet et al., 2015*).

In the sham session (inactive tDCS) there will be no stimulation. The procedure will be the same as the active tDCS but the machine will be turned off after 30 seconds.

tDCS it is not a medical device and it is considered a non-significant-risk device, meaning that it is a technique without expectation of any Serious Adverse Effect (*Bikson et al., 2016; Fregni et al., 2015*).

In the United States tDCS is not FDA approved. Some companies have an FDA (Food and Drug Administration) regulation status of “investigational” which limits the device to investigational use and not for medical treatment (*Fregni et al., 2015*). In the European Union, Canada, Brazil, Australia, and Singapore, specific tDCS products have been approved for treatment of various neuropsychiatric disorders. (*Fregni et al., 2015*).

Research centers worldwide are allowed to test tDCS in controlled clinical trials. A list of tDCS trials can be found here: clinicaltrials.gov

POST- Session (12)

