If the effects are experienced as uncomfortable to participants so that the stimulation will need to be stopped, we will not consider any data collected related to those participants. Participants have the right to not continue the study, in this case new participants will be enrolled for replacement.

8) Potential Benefits to Subjects

Participants may experience reduction in pain sensation, and will better understand their own pain and associated factors.

9) Vulnerable Populations

Vulnerable populations, i.e., children, individuals with moderate to severe cognitive impairment, prisoners of the penal system, and women who are pregnant will not be considered.

10) Setting

The study will take place at The Miami Project to Cure Paralysis, University of Miami.

11) Resources Available

[name] is the principal investigator of the Clinical Pain Research Laboratory of The Miami Project to Cure Paralysis. Her educational background is in cross-disciplinary pain research (pain physiology and pain psychology) and in the clinical management of chronic pain. She has performed human pain research for more than 26 years and in the field of spinal cord injury (SCI) for over 22 years. [name] has published 65 peer reviewed journal articles and written nine book chapters on pain and pain assessment. Her present research involves both qualitative and quantitative pain methodologies including quantitative sensory testing and MR spectroscopic brain imaging. She has adapted outcome measures used to classify and assess pain in other chronic pain populations to people with SCI and been instrumental in developing, presenting, and promoting the International SCI Pain Data Sets and the NINDS CDEs for SCI and Pain. She serves as the Chair or as a member in both National and International efforts to standardize pain outcome

measures and pain classification, and clinical guidelines related to pain. [name] has extensive interdisciplinary clinical pain research experience in persons with neurotrauma, including the use of a wide spectrum of pain outcome measurements and pain phenotyping.

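### Dropping all data from participants whose stimulation is stopped for discomfort lets a reaction to treatment decide who is compared, which can bias active versus sham

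*Combined protocol and SAP*

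**What the plan says.** The rule stands in Section 7, under Adverse Events and Serious Adverse Events associated with electrical stimulation. If stimulation must be stopped because a participant finds its effects uncomfortable, "we will not consider any data collected related to those participants". The next sentence concerns participants who choose not to continue: "in this case new participants will be enrolled for replacement". It does not say whether that covers people stopped for discomfort, or which arm a replacement joins.

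Other places that bear on it:

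- **Section 4, Arms and Interventions:** two arms of 8. Stimulation is given within an arm in Sessions 2-11.
- **Section 4, tDCS:** active current is 2 mA for 30 minutes per session. For sham, "The procedure will be the same as the active tDCS but the machine will be turned off after 30 seconds".
- **Section 4, Session 2-11:** up to 3 missed sessions are tolerated.
- **Section 7, tDCS risks:** the effects are described as minor and mild. "Other suggested but rare side-effects of tDCS include headache, nausea, and dizziness", and of nausea and dizziness it is said that "they have been illustrated to occur at nearly the same rate as sham stimulation". Before full current, "we will let them familiarizing for short time by applying a very small amount of current before to reach 2mA". On reporting, "we will keep record of any reported side effect".
- **Section 7, Data Analysis:** one sentence, leaving the choice between parametric and non-parametric methods to the distribution of the data.

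The protocol does not describe randomisation or say when allocation takes place.

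**The concern.** Two arms that were comparable at allocation stay comparable only if nobody is removed for something the treatment caused. Here the reason for removal is a reaction to the stimulation, and everything the participant contributed goes, including the baseline. If stopping differs between arms, and those who stop would have had a different pain change from those who continue, part of any active-sham difference is selection.

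The direction depends on facts the plan does not supply:

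- With equal stopping and the same outcome gap in both arms, the bias is zero.
- If more active participants stop and they would have done worse, it favours active.
- If more active participants stop and they would have done better, it works against active.

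The planned analysis cannot tell these cases apart, because it sets aside the outcomes that would show which one applies. In an arm of 8, one exclusion is 1/8 = 12.5% of the arm.

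That a stop comes after allocation is an inference from stimulation being given within an arm. A stop during the low-current familiarisation could come earlier, and excluding that person would then be a different matter.

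Two related points need tidying. Read literally, the exclusion of any data would also cover side effects and stops, which the same section promises to record. The rule is also uneven beside the missed-session allowance, although both can be followed. A participant who misses three sessions stays in with 7 × 30 = 210 of 300 minutes, while one stopped in the tenth session after 9 × 30 = 270 minutes is left out.

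**Working it through.** **The plan's own figures.** Section 4 plans 16 participants (8 per arm) and Section 14 gives a total of 20. Neither can be reproduced, because no significance level, power, effect size, SD or dropout rate is stated. I use 8 per arm and note where 10 per arm changes the result.

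**Assumptions (none of these values is in the documents).** Stopping on active, q_A, is 2-30%. Stopping on sham, q_S, is 0-5% and never above q_A. The correlation ρ between discomfort and a worse pain change is 0.3-0.7. There is no true treatment effect.

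**Step 1: bias formula.** Let discomfort be a standard normal score, with the top fraction q of an arm stopping. Removing them improves the mean change of those retained by ρ·φ(z)/(1−q) SD, where z is the 1−q normal quantile and φ the normal density. The bias is the active shift minus the sham shift.

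Example, 20% versus 5% with ρ = 0.5:

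- Active: 0.5 × 0.280/0.80 = 0.175.
- Sham: 0.5 × 0.103/0.95 = 0.054.
- Bias: 0.175 − 0.054 = 0.121 SD in favour of active.

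**Step 2: scale.** The standard error of the difference with 8 per arm is √(2/8) = 0.5 SD (with 10 per arm, √(2/10) = 0.447 SD).

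**Step 3: chance of a false significant result.** I assumed a two-sided t test at 5%, since the documents name neither a test nor a level. Rates come from simulation of 400,000 trials with 8 per arm and no replacement.

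| Active / sham stopping, ρ | Bias (SD) | Bias as % of SE | False result favouring active | Total two-sided |
|---|---|---|---|---|
| none | 0 | 0 | 2.5% | 5.0% |
| 2% / 0%, 0.3 | 0.015 | 3% | 2.7% | 5.0% |
| 5% / 0%, 0.5 | 0.054 | 11% | 3.1% | 5.1% |
| 5% / 0%, 0.7 | 0.076 | 15% | not run | not run |
| 10% / 5%, 0.5 | 0.043 | 9% | 3.0% | 5.1% |
| 20% / 5%, 0.5 | 0.121 | 24% | 4.0% | about 5.5% |
| 30% / 0%, 0.7 | 0.348 | 70% | about 8% | about 8.6% |
| 20% / 5%, −0.5 | −0.121 | −24% | 1.45% | about 5.4% |

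Over the whole grid the minimum is 0 (equal stopping) and the maximum 0.348 SD. If stoppers are replaced in the same arm, the total rates for 20% / 5% (ρ = 0.5) and 30% / 0% become about 5.6% and 10.5%, so assuming no replacement does not inflate the result.

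**Step 4: how often the rule would apply.** The chance that at least one of 8 active participants is left out is 1 − (1−q)^8: 15%, 34%, 57%, 83% and 94% for q = 2%, 5%, 10%, 20% and 30%. With 10 per arm it is 18%, 40%, 65%, 89% and 97%.

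**Step 5: a single exclusion.** Leaving out one of 8 whose change is d SD worse than the mean of the other 7 moves that arm's mean by d/8: 0.0625 SD for d = 0.5 and 0.125 SD for d = 1.

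**Step 6: bias left after the fix.** Suppose a share c of stoppers completes Session 12, the rest are treated as missing at random within arm, and Session 1 does not predict stopping. Each arm's shift becomes ρ·φ(z)(1−c)/(1−q+cq). For 20% versus 5% and ρ = 0.5:

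- c = 0: 0.121 SD.
- c = 50%: 0.078 − 0.026 = 0.051 SD (from unrounded terms).
- c = 75%: 0.037 − 0.013 = 0.024 SD.
- c = 100%: 0.

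**The case against.** The strongest reply is that the effect is small unless stopping is common. At 2-5% versus 0%, the total false-positive rate barely moves from 5%. The protocol describes the effects as minor, mild and temporary, which points to the low end of the range. That stands as a limit on size. It does not show that stopping would be equal: the near-sham comparison is made for nausea and dizziness, not for burning or tingling under the electrodes.

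The study is also a self-described pilot with tentative endpoints and no stated test, so error rates describe a test the plan does not specify. That is fair. The bias in the estimate does not depend on the test, however, and stops by arm are useful results for a pilot.

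It can be said, too, that the data are not destroyed, since Section 15 keeps a permanent archive of each participant's original data. That is correct, and a later analysis could use whatever was collected. But the archive neither brings those data into the planned analysis nor provides for a Session 12 visit after a stop.

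Three lesser points have some force. The text does not say whether ending one session triggers the rule or only permanent discontinuation. The word data may have been meant as outcome data only, in which case a clarifying phrase is enough. The comparison with the missed-session allowance shows unevenness, not a contradiction, and its 210 minutes assumes missed sessions are not made up.

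**Conclusion.** The concern holds. The plan contains an explicit rule that removes participants because of a reaction to the treatment being tested, and no other provision counteracts it. Followed as written, it can bias the active-sham comparison. Even with equal stopping in both arms, the result would describe only people who tolerate stimulation.

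How far it would bias this trial is unknown. Under the assumed ranges the bias is small against the 0.5 SD standard error when few people stop, about a quarter of a standard error at 20% versus 5%, and 0.35 SD only at the extreme of 30% versus 0%. A negative correlation reverses its sign. Confidence is high that the rule exists and can bias the result; no such confidence attaches to its size or direction. It should be fixed, since the remedy is cheap.

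**What to change.** Replace the exclusion sentence in Section 7 with wording such as:

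> All participants allocated to an arm are analysed in that arm, including those whose stimulation was stopped or who missed sessions; they are asked to complete Session 12. In the main analysis a missing Session 12 value is handled by one rule fixed before outcomes are compared by arm (for example, a mixed model for repeated measures using all observed Session 1 and Session 12 values). A no-change-from-baseline analysis and a completers-only analysis are sensitivity analyses. Side effects and stops are reported by arm for everyone who received any stimulation. Replacements are added to, and do not displace, the original participants.

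Also state when allocation happens relative to the low-current familiarisation, and define what counts as a stop when reporting stops by arm. Reporting side effects and stops for everyone also reconciles the exclusion rule with the promise to record side effects. The clinical decision to stop stimulation is unchanged.

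The cost is protocol wording, a few extra Session 12 visits and two sensitivity analyses. The estimate may be slightly less favourable because participants who stopped stay in. The main-analysis rule does not remove all bias if stoppers do not attend Session 12, so attendance after a stop matters more than the choice of model.
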